#### **4.1.1. General Methodology**

Participants who prematurely withdrew from study will not be replaced.

Continuous data will be summarized using descriptive statistics: n, mean, standard deviation (std), median, minimum, and maximum. Categorical data will be summarized as the number and percentage of participants in each category.

Unless stated otherwise, confidence intervals (CI) will be produced using 95% confidence levels.

[figure not shown]
#### **4.1.2. Baseline Definition**

For all endpoints the baseline value will be the latest pre-dose assessment with a non-missing value, including those from unscheduled visits. If a participant is in the ITT but hasn't taken a dose, they will be included in study population summaries on ITT set.

However, their change from baseline in CSS and **CCI** values will not be included in all the efficacy summary tables based on the CE sets. If time is not collected, Day 1 assessments are assumed to be taken prior to first dose and used as baseline.

If any participant is enrolled with a baseline CSS score < 2, it will be flagged as a protocol deviation and such participants will be excluded from the ITT and all CE analysis sets. If they have taken the dose, then they will be included in the safety analysis set.

**CCI**

If either baseline or post-baseline data is missing, then change from baseline will be set to missing at that visit/timewpoint.

The laboratory data, vital signs, ECG parameters are evaluated only at the baseline, but there could be assessments taken at unscheduled visits, which will only be included in the summary of worst-case post-baseline visit (only if there are at least 5 participants with data at unscheduled visits) and in the listings.

Unless otherwise stated, if baseline data is missing no derivation will be performed and baseline will be set to missing. If baseline data is missing, then change from baseline calculations will not be performed and will be set to missing.

### 4.1.3. Clinical Outcomes

The Clinical Outcome variables of a participant will be programmatically determined by comparing their total clinical signs and symptoms score at each scheduled timepoints except CCI [REDACTED] (i.e., 24 hours  $\pm$  4 hours, 48 hours  $\pm$  4 hours, 72 hours  $\pm$  4 hours and 96 hours  $\pm$  4 hours) to the score at Baseline. The clinical outcomes at CCI [REDACTED] are defined in Section 4.4.2.

The clinical outcomes are then used to define the primary and secondary response variables:

**Table 1 Clinical outcome at each Visit/Timepoint**

Definition Criteria	Outcome
Improvement of clinical signs and symptoms of uUTI present from Baseline, but not complete resolution, without the participant receiving other systemic antimicrobials for uUTI on/before each timepoint and without receiving other systemic antimicrobials for any other infections before each timepoint.	Clinical Improvement without Clinical Resolution
Improvement and complete resolution of clinical signs and symptoms of uUTI present from Baseline, without the participant receiving other systemic antimicrobials for uUTI on/before each timepoint and without receiving other systemic antimicrobials for any other infections before each timepoint.	Clinical Improvement with Clinical Resolution
Resolution of clinical signs and symptoms of uUTI present at Baseline (i.e., reduction of total CSS score to 0), without receiving other systemic antimicrobials for uUTI on/before each timepoint and without receiving systemic antimicrobials for other infections before each timepoint.	Clinical Resolution
No change is a change from baseline score of 0 at each timepoint, without the participant receiving other systemic antimicrobials for uUTI on/before each timepoint and without receiving systemic antimicrobials for other infections before each timepoint.	No Change
Worsening in clinical signs and symptoms from baseline (i.e., increase from baseline total CSS score $\geq 1$ ) and/or the participants receiving other systemic antimicrobials for uUTI on/before each timepoint.	Clinical Worsening
(1) The baseline score is missing, (unless clinical worsening outcome criteria were met) or (2) Post baseline assessment is missing (unless clinical worsening outcome criteria were met): 
 
• The post-baseline visit occurred but assessment is missing, or
 
• The post-baseline visit not occurred, or
 
	Unable to determine

Definition Criteria	Outcome

 
The post-baseline assessment is out of visit window, or
 
 
(3) The participant received any other systemic antimicrobials for other infections before the post-baseline timepoint (unless clinical worsening outcome criteria were met)
	

Note: Each timepoint is defined based on the date/time from the first dose.

Timepoints are 24 hours  $\pm$  4 hours, 48 hours  $\pm$  4 hours, 72 hours  $\pm$  4 hours, 96 hours  $\pm$  4 hours.

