 - Participants unable to take 2 doses as prescribed before the CSS assessment at 24 hours (± 4 hours) (Principal Stratum Strategy). Interest lies in the group of participants who complied with the 2 doses as prescribed before the CSS assessment at 24 hours (± 4 hours).
 - A participant using other systemic antimicrobials (for uUTI or other infections) on or before the CSS assessment at 24 hours (± 4 hours) (Composite Strategy). This ICE is incorporated into the definition of the endpoint.
- The population-level summary to be estimated is percentage of participants who achieve clinical symptom improvement and its 95% Exact Binomial CI.

RATIONALE FOR PRIMARY ESTIMANDS:

- Interest lies in evaluating study intervention benefit through a decrease in CSS total score in participants who achieve 100% compliance to study intervention before the CSS assessment at 24 hours (± 4 hours).
- Participants who take other antimicrobials for uUTI indicate lack of treatment benefit and will not be able to achieve symptom improvement (i.e., treatment failures). Participants who take other antimicrobials for other infections might confound the outcome by improving the symptoms. Therefore, such participants are also set to treatment failures.

SUPPLEMENTARY ESTIMAND FOR PRIMARY ENDPOINT:

A supplementary estimand will be considered if **CCI** participants are not able to comply with the 2 doses as prescribed before the CSS assessment at 24 hours (± 4 hours).

The additional clinical question of interest is to assess symptom improvement without the need for other systemic antimicrobials in participants at 24 hours (± 4 hours) after the initial dose of gepotidacin.

The supplementary estimand is described by the following attributes:

- The population is female participants aged ≥ 12 years with suspected uUTI.
- The endpoint is achieving clinical symptom improvement, defined as a decrease from Baseline in CSS total score of at least 1 point at 24 hours (± 4 hours), without the need for other systemic antimicrobials.
- The treatment condition is gepotidacin 1500 mg BID.
- The ICEs and estimand strategies are as follows:
 - Participants unable to take 2 doses as prescribed before the CSS assessment at 24 hours (± 4 hours) (Treatment Policy Strategy). Interest lies in the treatment effect regardless of compliance with the study intervention.

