6.9. Prior and concomitant therapy

Any medication or vaccine (including over-the-counter or prescription medicines, vitamins, and/or herbal supplements) that the participant is receiving within 30 days prior to the Baseline Visit or receives during the study must be recorded in the eCRF. In addition, any antibiotic use within 6 months prior to the Baseline Visit or during the study must be recorded in the eCRF. The concomitant therapy name must be recorded in the eCRF along with the following:

- Reason for use
- Dates of administration including start and end dates
- Dosage information including dose and frequency

The medical monitor is to be contacted if there are any questions regarding concomitant or prior therapy.

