#### **Endpoint:**

- The primary endpoint is achieving clinical symptom improvement, defined as a decrease from Baseline in CSS total score of at least 1 point at 24 hours ( $\pm 4$  hours), without the need for other systemic antimicrobials on or before the time of this assessment.

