#### **Intercurrent Events and Strategies:**

- The intercurrent events (ICEs) and estimand strategies are:
  1. Participants unable to take 2 doses as prescribed before the CSS assessment at 24 hours ( $\pm 4$  hours) (Principal Stratum Strategy). Interest lies in the group of participants who complied with the 2 doses as prescribed before the CSS assessment at 24 hours ( $\pm 4$  hours).

2. A participant using other systemic antimicrobials, for uUTI on or before the CSS assessment at 24 hours ( $\pm 4$  hours) and/or for other infections before the CSS assessment at 24 hours ( $\pm 4$  hours) (Composite Strategy). These ICES are incorporated into the definition of the endpoint.

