**Intercurrent Events and Strategies:**

- The intercurrent events (ICEs) and estimand strategies are:
  1. Participants unable to take  $\geq 80\%$  doses of gepotidacin up to each time point i.e., 24 hours ( $\pm 4$  hours), 48 hours ( $\pm 4$  hours), 72 hours ( $\pm 4$  hours), and 96 hours ( $\pm 4$  hours) (Treatment Policy Strategy). Interest lies in all participants regardless of compliance with study intervention.
  2. A participant using other systemic antimicrobials (for uUTI or other infections) on or before 48 hours ( $\pm 4$  hours), 72 hours ( $\pm 4$  hours), and 96 hours ( $\pm 4$  hours) (Composite Strategy). This ICE is incorporated into the definition of the endpoint.
  3. Study intervention discontinuation (due to any reason) (Treatment Policy Strategy). Interest lies in the treatment effect regardless of study intervention discontinuation.

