Concomitant Medications including Antibiotics and Prohibited medications/Medical History	
 
• Partial dates for any concomitant medications recorded in the CRF will be imputed using the following convention and the recorded partial date will be displayed in listings:
 
 
 
 Missing start day	 
If study intervention start date is missing (i.e. participant did not start study intervention), then set start date = 1st of month.
 
Else if study intervention start date is not missing:
 
 
• If month and year of start date = month and year of study intervention start date, then 
 
– If stop date contains a full date and stop date is earlier than study intervention start date, then set start date= 1st of month.
 
– Else set start date = study intervention start date.
 
 
 
 
Else set start date = 1st of month.
 	
 
 Missing start time	 
Midnight 0:00:00 will be used for concomitant medications with missing start time if treatment start date is not same as the concomitant medication start date.
 	
 
		Missing start day	
If study intervention start date is missing (i.e. participant did not start study intervention), then set start date = 1st of month.
 
Else if study intervention start date is not missing:
 
 
• If month and year of start date = month and year of study intervention start date, then 
 
– If stop date contains a full date and stop date is earlier than study intervention start date, then set start date= 1st of month.
 
– Else set start date = study intervention start date.
 
 
 
 
Else set start date = 1st of month.
	Missing start time	
Midnight 0:00:00 will be used for concomitant medications with missing start time if treatment start date is not same as the concomitant medication start date.

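### The antimicrobial-failure part of the endpoints has no single cut-off: the primary estimand stops at the CSS assessment, SAP Table 1 at a timepoint counted from first dose

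*SAP*

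**What the plan says.** **Primary estimand.** Protocol Section 3 lists as a composite intercurrent event (ICE): "A participant using other systemic antimicrobials (for uUTI or other infections) on or before the CSS assessment at 24 hours". The SAP 1.1 endpoint text agrees: "without the need for other systemic antimicrobials on or before the time of this assessment". The SAP 1.1 ICE text keeps the CSS assessment as the reference but splits by indication: on or before it for uUTI, but "for other infections before the CSS assessment at 24 hours" for the rest.

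**Programmed outcome.** SAP 4.2.1 and 4.3.1.1 derive the responses from SAP Table 1 (Section 4.1.3). Table 1 requires improvement without "receiving other systemic antimicrobials for uUTI on/before each timepoint and without receiving other systemic antimicrobials for any other infections before each timepoint". Its note reads "Each timepoint is defined based on the date/time from the first dose" and lists the timepoints as 24, 48, 72 and 96 h, each ±4 h.

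**Secondary endpoints.** The SAP 1.1 endpoint text says on or before the assessment for any use. The main secondary ICE says on or before the timepoint for uUTI and before it for other infections. The supplementary secondary ICE goes back to one rule for both: "A participant using other systemic antimicrobials (for uUTI or other infections) on or before 48 hours".

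**Other places.** Protocol Tables 4 and 5 use *prior to* the assessment for other infections, and *prior to or at* the timepoint for uUTI. SAP 4.2.3 (multiple imputation) refers to the timepoint of the CSS assessment.

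**Dates and times.** Protocol 6.9 asks for "Dates of administration including start and end dates" and lists no clock time. SAP 6.3.8 says "Midnight 0:00:00 will be used for concomitant medications with missing start time", provided the start date is not the first-dose date.

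**The concern.** Two things differ between these texts: the reference time (the CSS call, or a time counted from first dose) and whether the boundary itself is included. The first matters more. A participant whose score improved, and who took another antimicrobial between her call and the window limit, or between 24 h and a later call, can be a success or a failure depending on which text is programmed. In the second situation, Table 1 read at 24 h would credit gepotidacin with a score obtained after another antimicrobial had started.

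The route exists in the plan: the Schedule of Activities allows an alternative antibiotic at an Unscheduled Visit arranged for lack of response. The study is open-label and single-arm, and its primary result is one percentage. If the failure rule allows several readings, the choice falls to whoever programs it, after data exist.

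**Working it through.** **Plan's own figure.** Protocol 1.1 gives 82 evaluable participants, a 74% rate and a 95% CI half-width of approximately ≤10%. The exact (Clopper-Pearson) half-width at n = 82 and p = 0.74 is 9.97%; at n = 81 it is 10.03%. The figure reproduces, and 82 is the smallest n that meets it.

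**Same participant, different texts.** Each case assumes a CSS fall of at least 1 point and a first dose at 10:00. Times are hours from first dose. Protocol Table 4 is read at 24 h for uUTI.

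| Case | Protocol 3 ICE; SAP 1.1 endpoint | SAP 1.1 ICE | Protocol Table 4 | SAP Table 1 at 24 h | SAP Table 1 at 28 h |
|---|---|---|---|---|---|
| A. CSS 21 h, uUTI antimicrobial 23 h | success | success | failure | failure | failure |
| B. CSS 27 h, uUTI antimicrobial 25 h | failure | failure | success | success | failure |
| C. CSS 24 h, other-infection antimicrobial at 24 h exactly | failure | success | success | success | failure |
| D. CSS 24 h, uUTI antimicrobial 30 h, time recorded | success | success | success | success | success |
| E. As D, time missing | failure | failure | failure | failure | failure |

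A and B show the reference-time conflict, which can go either way. C shows the boundary conflict, which needs an exact tie between antimicrobial and CSS. In E the start (16:00 on the CSS date) becomes 00:00 that day, 14 h after first dose, and so falls before the call under every text.

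**Effect per participant.** 1/82 = 1.22 points.
- 61/82 = 74.4% (exact 95% CI 63.6 to 83.4)
- 60/82 = 73.2% (62.2 to 82.4)
- 59/82 = 72.0% (60.9 to 81.3)

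**How many (assumptions, not document figures).** Take the CSS time as uniform on 20 to 28 h.
- Antimicrobial start uniform on 4 to 28 h: the share classed differently by a 28 h cut-off than by the CSS time is mean(28 − CSS)/24 = 4/24 = 16.7%. By a 24 h cut-off it is mean|CSS − 24|/24 = 2/24 = 8.3%.
- Start 1 to 8 h after the call, uniform: the share falling by 28 h is (1/7)(1/8)(7²/2) = 43.75%.
- Assume 2% to 5% start another antimicrobial around the visit: 82 × 0.02 = 1.6 and 82 × 0.05 = 4.1, so about 2 to 4 participants.
- Only improvers can change class. At the overall 74%, 2 to 4 × 0.74 × 0.167 gives about 0.25 to 0.5 participants, and 2 to 4 × 0.74 × 0.4375 gives about 0.65 to 1.3.

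Participants who switch for poor relief should improve less often than 74%, so these counts lean high.

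**The case against.** **Table 1 may simply mean the call.** SAP 4.3.1 speaks of the time of the assessments as defined in Table 1, SAP 4.2.3 speaks of the timepoint of the CSS assessment, and the table title pairs visit with timepoint. These favour the CSS time. They do not override the table's own note, and in its clinically evaluable (CE) sets the SAP separates the two: before the CSS if available, otherwise before the window end from first dose. Table 1 lacks that sentence.

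***On or before* against *before* is nearly empty.** With recorded times this is right; it needs an exact tie. Nor is a different rule for uUTI and other infections an error in itself, since Protocol Tables 4 and 5 have one. The fault is that the endpoint and ICE texts do not follow it consistently.

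**Midnight imputation.** A reader might infer that every antimicrobial started after the call on the CSS date is backdated. SAP 6.3.8 does not say that: it acts only on a missing time, off the first-dose date. The notes to SAP 6.3.3.1 use time to classify same-day medication, so times may be collected. The eCRF is not available, so the frequency is unknown. The rule moves participants only toward failure.

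**Main and supplementary secondary results.** A reader might also infer that these would use different endpoint rules because their ICE texts differ. SAP 4.3.1.1 derives the responses from Table 1, the two endpoint texts match, and the supplementary analysis is conditional. The text conflict stands; a difference in the results does not follow.

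**Conclusion.** The inconsistency is in the text and reaches the primary endpoint. The estimand and the table that programs it can classify the same improved participant differently, in either direction. The likely size is small: 1.22 points per participant at n = 82, and about one participant or fewer at 24 h under the assumed switch rate and timings. The true number cannot be derived from the documents.

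Two larger readings are not supported. Treating every switch as a possible reclassification would suggest several points on the primary rate, but participants who did not improve are failures under every text. One reclassification takes the half-width from 9.9 to 10.1 points, but the target is stated as approximate and no hypothesis is tested, so this is immaterial. The sample size is unaffected.

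The point is still worth correcting before database lock, because it concerns a stated rule for the primary endpoint and the correction is cheap.

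**What to change.** State in SAP Table 1 that *timepoint* means the date/time of the CSS used for that timepoint or, if that CSS is missing, the upper window limit. This is the anchor of the CE sets. In the main analysis a missing CSS is already a failure, so the fallback matters only for the imputation step in SAP 4.2.3.

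Use one rule in SAP 1.1, Table 1, 4.2.3 and 4.3.1, and align Protocol 3 and 8.2.1 at the next amendment: failure if any other systemic antimicrobial, for uUTI or another infection, is used from the first dose up to and including that time. Word it as use, not start. SAP 6.1.4 separately tracks antibiotics begun before treatment and continued, and SAP 6.3.8 sets a Day 1 start with missing time to the first-dose time; a rule limited to starts after the first dose would let both escape.

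Query the start time of any antimicrobial that starts on a CSS date. If it stays missing, keep the participant as a failure in the main analysis, report the count, and show the rate with those participants scored by their CSS.

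Cost: SAP wording, a protocol alignment at the next amendment, a few site queries and one extra sensitivity line.

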## 4.2. Primary Endpoint(s) Analyses

The primary estimand and supplementary estimands for the primary endpoint are defined in Section 1.1.

### 4.2.1. Definition of primary endpoint

The primary efficacy endpoint is achieving clinical symptom improvement (including clinical resolution). In this study, a participant will be considered to have clinical improvement (including clinical resolution) outcome if they attain either a “Clinical Improvement with Clinical Resolution” outcome or, a “Clinical Improvement without Clinical Resolution” outcome as defined in Table 1. And otherwise, as not improved/failure if they have any other outcomes.

Individual scores will be recorded by a study physician or otherwise appropriately medically trained staff, as recorded in the delegation log. Clinical symptom score (CSS) of acute cystitis participants will be recorded as per the protocol defined SoA using the following scoring system:

Clinical Signs and Symptoms	None	Mild  Symptom is easily tolerated, causing minimal discomfort, and not interfering with everyday activities	Moderate  Symptom is sufficiently discomforting to interfere with normal everyday activities	Severe  Symptom prevents normal everyday activities
	SCORE 0	SCORE 1	SCORE 2	SCORE 3
Dysuria a				
Frequency				
Urgency				
Lower abdominal				

Clinical Signs and Symptoms	None	Mild	Moderate	Severe
	SCORE 0	SCORE 1	SCORE 2	SCORE 3
or suprapubic pain				

a. Dysuria is defined as pain or burning when passing urine.

- The clinical signs and symptoms include dysuria, frequency, urgency, and lower abdominal or suprapubic pain. Each of the signs and symptoms will be scored from 0 to 3.
- At Baseline, the participant must present with at least 2 signs and symptoms and have a total cumulative symptom score  $\geq 2$ . The total cumulative symptom score is derived by summing the score for each individual sign and symptom. If any individual sign and symptom scores are missing, then total symptom score will also be missing. If the participant is missing baseline assessment, they will be considered 'Unable to determine' (refer [Table 1](#)) for outcome at the respective visit.
- The clinical symptoms improvement will be programmatically determined by comparing the total scores of the signs and symptoms of acute cystitis at the 24 hours ( $\pm 4$  hours) to those present at baseline as shown in [Table 1](#).

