#### 4.2.2. Main analytical approach for primary endpoint

Participants achieving the primary efficacy endpoint of clinical symptom improvement with resolution at 24 hours  $\pm 4$  hours (refer definition in Section [4.2.1.](#)) will be estimated by frequency and percentage using CE24 set.

Exact Binomial (Clopper Pearson) 95% confidence limits for percentage of participants with clinical symptom improvement at 24 hours  $\pm 4$  hours will be computed. Participants who are not able to complete the CSS assessment at 24 hours ( $\pm 4$  hours) will be considered as 'treatment failure' and included as 'not improvers' in primary analysis.

A stacked bar graph will be produced for:

- Individual component of clinical symptoms by severity. (none/mild/moderate/severe) at 24 hours and baseline which will be presented using the ITT and CE24 sets respectively.
- Total clinical symptom score categories classified as (<2, 2-5, 6-8, 9-12) will be presented by visits using the ITT and CE24 sets.

- Percentage of participants with clinical improvement, clinical resolution, Clinical worsening and UTD by visits for CE24 set.

A descriptive summary will be presented for CSS total and individual scores (Dysuria, Frequency, Urgency, and Lower abdominal or Suprapubic pain) including n, mean, standard deviation (std), median, minimum, and maximum at each timepoint (24 hours  $\pm$  4 hours, 48 hours  $\pm$  4 hours, 72 hours  $\pm$  4 hours and 96 hours  $\pm$  4 hours) for the ITT set. Participants listings for clinical outcome and response will also be produced for ITT set.

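### A partly completed CSS counts as failure even when the observed items already prove improvement: a downward bias, probably small, with a simple remedy in the main analysis

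*SAP*

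**What the plan says.** The CSS has four items, and "Each of the signs and symptoms will be scored from 0 to 3" (SAP 4.2.1). SAP 1.1 makes the primary endpoint improvement, "defined as a decrease from Baseline in CSS total score of at least 1 point at 24 hours", without other systemic antimicrobials. The derivation in SAP 4.2.1 works on totals: "The clinical symptoms improvement will be programmatically determined by comparing the total scores of the signs and symptoms of acute cystitis". For incomplete forms it adds: "If any individual sign and symptom scores are missing, then total symptom score will also be missing".

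Table 1 in SAP 4.1.3 assigns the class *Unable to determine* when the baseline score is missing, or when "The post-baseline visit occurred but assessment is missing". SAP 4.2.1 accepts the two improvement classes as success, "And otherwise, as not improved/failure if they have any other outcomes". SAP 4.2.2 keeps participants without a completed CSS in the denominator, "included as 'not improvers' in primary analysis". The same missing-equals-failure convention governs the supplementary analyses (SAP 4.2.4, 4.3.1.4), the secondary analyses (SAP 4.3.1.2) and the general rule in SAP 6.3.10. Protocol 9.3.2.1 and 9.3.3 agree with it.

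The sensitivity analysis in SAP 4.2.3 imputes the yes/no outcome by logistic regression on baseline covariates (list redacted), assuming missing at random, with 1000 imputations. SAP 4.3.1.3 reuses it with one further covariate, also redacted. No visible text uses the observed items of a partial form.

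**The concern.** Counting a missing outcome as failure is an ordinary conservative convention when the outcome is unknown. Here it also catches participants whose outcome is known. The endpoint needs a fall of only 1 point, and a missing item can add no more than 3, so three observed items can settle the question whatever the fourth would have been. Such a participant meets the endpoint definition but is counted against it.

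The study has one arm and no hypothesis test (SAP 2), so the estimated rate and its interval are the main result. Settled improvers counted as failures pull that estimate down.

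**Working it through.** **Inputs.** Four items scored 0 to 3 and a threshold of 1 point (SAP 1.1, 4.2.1); 82 evaluable participants and an assumed 74% rate (Protocol 1.1); Clopper-Pearson 95% interval (SAP 4.2.2). The number of partial forms is not in the documents, so it is varied below.

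**1. The plan's precision figure.** With n = 82 and a rate of 74%, the Clopper-Pearson half-width is 9.97 points (61/82 gives 9.92). With n = 81 it is 10.03. The stated target of about 10% or less is reproduced.

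**2. When the observed items settle improvement.** Let B be the baseline total and S the sum of the three observed 24-hour items. The 24-hour total is at most S + 3. Improvement is certain if S + 3 ≤ B − 1, that is, **S ≤ B − 4**. This is impossible at B = 2 or 3 and possible from B = 4 upward.

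Example: B = 9; items 1, 1, 0 and one missing. S = 2, so the total lies between 2 and 5 and the fall between 4 and 7. She has improved, and the SAP counts her as a failure.

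If one baseline item is missing instead, improvement is certain when the 24-hour total is at least 1 below the sum of the three observed baseline items. She is *Unable to determine* at all four time points.

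**3. How often a partial form would be settled.** Take all score patterns in which no item worsens and the total falls, weighted equally, and delete one 24-hour item. This is illustrative only, because the documents give no item distribution.

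| Baseline total | Settled as improved |
|---|---|
| 4 | 248/1116 = 22% |
| 6 | 2624/4320 = 61% |
| 8 | 6300/7496 = 84% |
| 10 | 5184/5464 = 95% |

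**4. Effect on the primary rate.** Assume 61 of 82 truly improve, of whom k are settled improvers with a partial form:

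| k | Reported | 95% CI (%) | Half-width (points) |
|---|---|---|---|
| 0 | 61/82 = 74.4% | 63.6 to 83.4 | 9.92 |
| 1 | 60/82 = 73.2% | 62.2 to 82.4 | 10.06 |
| 2 | 59/82 = 72.0% | 60.9 to 81.3 | 10.19 |
| 4 | 57/82 = 69.5% | 58.4 to 79.2 | 10.42 |

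Each one costs 1/82 = 1.22 points. The bound restores 74.4% in every row.

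**5. Resolution.** Three observed zeros cannot prove a total of 0, and any observed item above 0 already means not resolved. A missing post-baseline item therefore changes nothing in the main analysis of resolution. The one corner left is a missing baseline item with a complete post-baseline total of 0.

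**6. Bounds followed by the planned imputation.** Among partial forms with the same baseline covariates, let a be the share settled as improved, b the share settled as not improved, u = 1 − a − b the rest, and q the true improvement rate in the rest. The true rate is R = a + uq. With items missing at random, a baseline-only model predicts about R.

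- Planned imputation, all partial forms imputed: R, unbiased.
- Bounds first, then the rest imputed at R: a + uR. Bias = u(R − q) = u[a(1 − q) − bq].

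The bias is zero only if u = 0 or a/(a + b) = q, and it can have either sign. In simulations with assumed item distributions, true rates among partial forms of 0.70, 0.84 and 0.61 became 0.74, 0.90 and 0.59. In another run (true rate 72.2%), the planned imputation returned 72.2%. Bounds followed by imputation gave 76.6%, because the remaining participants improved in 62% but were imputed at 72%. With 4 partial forms in 82, that error would move the overall rate by 4.4 × 4/82 = 0.2 points.

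**The case against.** Failure for an incomplete CSS is prespecified in the protocol, applied consistently in the SAP, and conservative. Nothing shows that the case will occur. Under Protocol Appendix 1, trained staff read the criteria aloud by telephone and determine the score, so a participant who is reached would normally answer all four questions. Partial forms would also be visible: SAP 4.2.2 reports n for the total and for each item, and lists outcomes. Parts of Appendix 1 and the imputation covariates are redacted, so a rule for incomplete items cannot be excluded.

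Most of this stands as a limit on size. It does not justify recording a known success as a failure, and showing partial forms in listings does not correct the estimate.

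A reader might infer three stronger things that the documents do not support.

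- **That the planned multiple imputation is biased because it ignores the observed items.** It gives a settled improver only partial credit, but across partial forms it is unbiased if items are missing at random given the covariates. A shortfall such as 57/78 = 73.1% against 74.4% appears only if every partial form is assumed to belong to a settled improver.
- **That the bounds can simply be applied before imputation at no cost.** Step 6 shows that this can bias the sensitivity analysis.
- **That a large share of participants is affected.** Any percentage of settled forms, including those in step 3, depends on assumed score patterns and on a partial form existing at all.

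**Conclusion.** The point holds for the main, secondary and supplementary analyses of improvement. On the visible text, a participant with a partial CSS is counted as a failure even where the observed items prove a fall of at least 1 point. With one 24-hour item missing, this requires an observed sum of at most the baseline total minus 4, hence a baseline total of at least 4, and no disqualifying antimicrobial.

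Each case lowers the primary rate by 1.2 points on 82 participants. The number of cases is unknown and probably small, and the bias is downward. This is a derivation rule that discards information, not a contradiction between protocol and SAP. It is worth correcting but is not a threat to the study's conclusion.

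**What to change.** **Main, secondary and supplementary improvement analyses.** Before classifying a partial form, set missing post-baseline items to 3 and missing baseline items to 0. If the resulting post-baseline total is still at least 1 point below the baseline total, and no disqualifying antimicrobial was taken, count the participant as improved. Otherwise keep missing as failure.

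**Multiple-imputation sensitivity analyses.** Do not apply the bounds and then impute the rest from baseline covariates only. Impute the missing item or items given the observed items at that visit and the baseline data, then derive total, improvement and resolution. Settled outcomes are then kept automatically, including not resolved whenever an observed item is above 0. Adding the observed-item sum to the existing logistic model is an alternative, with settled outcomes held fixed. It needs separate handling for participants with no CSS at that visit, because SAP 4.2.3 classes anyone with a missing covariate as a failure.

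**Reporting.** Tabulate the number of partial CSS forms by visit, and how many the bound settles.

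**Cost.** One derivation rule, slightly more programming and a modified imputation model, specified before database lock. No new data are needed, and if no partial forms occur the main results do not change.
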